6.0 Study Procedures

Screening/Consent visit (Day 1 of Study Participation): Potential participants will be screened to determine eligibility for participation in the study. This screening, supervised by the study physician, will include evaluation to characterize the nature of the chronic back pain and to confirm eligibility to engage in the exercise manipulation. Potential participants will also be screened for the exercise exclusion criteria by answering questions related to moderate-vigorous physical activity from the CDC Behavioral Risk Factor Surveillance Survey to classify potential subjects as active or inactive. Following informed consent, participants will complete study questionnaires. Questionnaires will include assessment of occupational status (Employed, Not Working, Disabled), and for working individuals, number of hours worked per week and nature of the job for use as an additional measure of activity. Participants will also complete the International Physical Activity Questionnaire (IPAQ) to gather additional relevant physical activity

information prior to beginning participation in the study, to supplement diary-based data regarding exercise activity. Questionnaires assessing factors related to back pain, anger, depression, anxiety, pain coping, and pain medication responses will be completed. Participants will then complete the 5-day pre-manipulation electronic diary assessment procedures.

Pre-Manipulation 5 day Electronic Diary Monitoring Period (Days 2-6): Daily chronic back pain intensity will be assessed for 5 days pre-manipulation via an electronic pain diary using handheld Palm® Zire 22 PDAs, running the Palm OS platform. To provide a representative sampling of daily back pain intensity, participants will be prompted by an audible alert at 9am and again at 6pm daily. At each prompting, participants will be asked to electronically record ratings of their current back pain, recent sleep, activity levels, and mood using 9 point numeric scales. Participants will begin the laboratory portion of the study following completion of this first diary monitoring period.

Lab Visit 1 (≈Day 7): Participants will undergo a urine screening for opiate use (females will also be screened for pregnancy); complete psychometric instruments; training for heat pain stimulus (Visit 1 only); 5 minutes of seated rest; participants rate their current low back pain intensity; nurse inserts i.v. cannula; nurse obtains a 4ml blood sample via cannula to assess endocannabinoid levels (Visits 1 and 4 only); nurse administers randomized drug dose #1. Administration of randomized drug dose #1 (specific drug protocol is summarized below) will be followed by 10 minutes of seated rest to achieve peak drug levels; participant rating of chronic pain intensity; thermal pain task #1 (described in detail below); assess thermal pain intensity; assess drug side effects and psychoactive effects; nurse administers randomized drug dose #2. Administration of drug dose #2 will be followed by 10 minutes of seated rest to achieve peak drug levels; participant rating of chronic pain intensity; thermal pain task #2; assess thermal pain intensity; assess drug side effects and psychoactive effects; nurse administers randomized drug dose #3. Administration of drug dose #3 will be followed by 10 minutes of seated rest to achieve peak drug levels; participant rating of chronic pain intensity; thermal pain task #3; assess thermal pain intensity; assess drug side effects and psychoactive effects; nurse administers randomized drug dose #4. Administration of drug dose #4 will be followed by 10 minutes of seated rest to achieve peak drug levels; participant rating of chronic pain intensity; thermal pain task #4; assess thermal pain intensity; assess drug side effects and psychoactive effects; seated rest until side effects remit.

(each session ≈ 5 days apart)

Lab Visit 2: Participants will undergo a urine screening for opiate use (females will also be screened for pregnancy); 5 minutes of seated rest; participants rate their current low back pain intensity; nurse inserts i.v. cannula; nurse administers randomized drug dose #1. Administration of randomized drug dose #1 will be followed by 10 minutes of seated rest to achieve peak drug levels; participant rating of chronic pain intensity; thermal pain task #1; assess thermal pain intensity; assess drug side effects and psychoactive effects; nurse administers randomized drug dose #2. Administration of drug dose #2 will be followed by 10 minutes of seated rest to achieve peak drug levels; participant rating of chronic pain intensity; thermal pain task #2; assess thermal pain

intensity; assess drug side effects and psychoactive effects; nurse administers randomized drug dose #3 . Administration of drug dose #3 will be followed by 10 minutes of seated rest to achieve peak drug levels; participant rating of chronic pain intensity; thermal pain task #3; assess thermal pain intensity; assess drug side effects and psychoactive effects; nurse administers randomized drug dose #4. Administration of drug dose #4 will be followed by 10 minutes of seated rest to achieve peak drug levels; participant rating of chronic pain intensity; thermal pain task #4; assess thermal pain intensity; assess drug side effects and psychoactive effects; seated rest until side effects remit.

(each session \approx 5 days apart)

Lab Visit 3: Participants will undergo a urine screening for opiate use (females will also be screened for pregnancy); 5 minutes of seated rest; participants rate their current low back pain intensity; nurse inserts i.v. cannula; nurse administers randomized drug dose #1. Administration of randomized drug dose #1 will be followed by 10 minutes of seated rest to achieve peak drug levels; participant rating of chronic pain intensity; thermal pain task #1; assess thermal pain intensity; assess drug side effects and psychoactive effects; nurse administers randomized drug dose #2. Administration of drug dose #2 will be followed by 10 minutes of seated rest to achieve peak drug levels; participant rating of chronic pain intensity; thermal pain task #2; assess thermal pain intensity; assess drug side effects and psychoactive effects; nurse administers randomized drug dose #3 . Administration of drug dose #3 will be followed by 10 minutes of seated rest to achieve peak drug levels; participant rating of chronic pain intensity; thermal pain task #3; assess thermal pain intensity; assess drug side effects and psychoactive effects; nurse administers randomized drug dose #4. Administration of drug dose #4 will be followed by 10 minutes of seated rest to achieve peak drug levels; participant rating of chronic pain intensity; thermal pain task #4; assess thermal pain intensity; assess drug side effects and psychoactive effects; seated rest until side effects remit.

Exercise Manipulation (Weeks 4 – 10 of study participation): Following the third laboratory visit, participants will be randomly assigned to study condition, stratified by recruitment source (clinic vs. community). Participants randomly assigned to the exercise condition will then complete the 18 session aerobic exercise manipulation supervised by an ACSM-certified personal trainer at the Dayani Center (3 exercise sessions per week for 6 weeks). Participants assigned to the control condition will not undergo any manipulation during this 6 week period, and will be asked to continue their current activity levels and not engage in any additional exercise activity during the study period (confirmed via electronic diary). All subjects will complete brief pain and psychosocial questionnaires once weekly by phone.

Lab Visits 4 – 6 (\approx Weeks 11-12): Identical procedures to those described above for Lab Visits 1-3. Drug order is again randomized and counterbalanced.

Post-Manipulation 5 day Electronic Diary Monitoring Period (\approx Week 11, between Lab Visits 4-5): Identical to pre-manipulation electronic diary procedures described above.

Description of Laboratory Visit Procedures:

All laboratory procedures will be conducted with participants seated upright in a comfortable chair. Each participant's series of three laboratory sessions (placebo, naloxone, morphine) carried out both pre- and post-manipulation will be scheduled within an ≈ 10 day period, at the same time of day to control for variance due to circadian rhythms.

Study Drug Protocol: Study drugs will be administered (in double-blind fashion) in randomized, counter-balanced order. The assigned study drug will be administered within a given session over 4 infusions (2 min each) according to the following protocol, depending on the assigned drug for that visit: 1) 4 doses of saline placebo (20ml each), 2) an 8mg dose of naloxone (in 20ml saline vehicle), followed by saline, 4mg naloxone, and saline, or 3) morphine sulfate (0.03 mg/kg in 20ml saline vehicle initially, followed by 3 incremental doses of 0.02mg/kg each). To avoid excessive morphine doses (and increased side effect risks) for individuals who are obese, a modified weight adjustment will be employed for individuals more than 30% over ideal body weight based on subjects' observed weight in clinic compared to appropriate ideal body weight for males (50kg+2.3kg for each inch over 5 feet) or females (45.5kg +2.3kg for each inch over 5 feet) [from <http://www.globalrph.com/>]. For individuals meeting this obesity criterion, morphine dosage will be based on Adjusted Body Weight rather than actual body weight, as calculated by: $\text{Ideal Body Weight} + 0.4 (\text{actual weight} - \text{Ideal Body Weight})$.

Thermal Pain Task Procedures: The heat pain task will use a computerized Medoc TSAII NeuroSensory Analyzer to assess heat pain threshold and tolerance using an ascending method of limits protocol. Ten minutes after each drug infusion, three trials will be conducted for heat pain threshold and three trials for heat pain tolerance, with each trial conducted sequentially at one of three non-overlapping sites on the non-dominant ventral forearm. An interval of 30 seconds between successive stimuli will be employed. For pain threshold trials, the probe will start at an adaptation temperature of 32°C, with temperature increasing at a ramp rate of 0.5°C/sec until the participant indicates that the stimulus has begun to feel "painful." For each tolerance trial, the probe will start at an adaptation temperature of 40°C, with the temperature increasing at a ramp rate of 0.5°C/sec until the participant indicates maximum tolerance has been reached. Immediately upon completion of the final heat pain tolerance trial at each drug dosage, participants will be asked to rate the pain just experienced using the MPQ.

Patient instructions for this task: "During this next part of the experiment, I'll be testing your sensitivity to the heat pain stimulus I showed you earlier. First we will do the pain threshold test, which asks you to indicate when the heat FIRST begins to feel painful. The probe will start out slightly cool, and when we start the test, you will hear a beep and the probe will begin feeling warm and the temperature will steadily increase. During the test, keep your finger on the LEFT button of this mouse, and press this button the moment the heat first becomes painful. Keep in mind that this is not a test of how much pain you can tolerate, but rather, we want to know the instant at which the heat stimulus first feels painful. Please stay alert and concentrate throughout the test. Pressing the button will turn the heat off, so don't press it until the heat first feels painful to you. We will do this test several times. Do you have any questions about this test? The next test we will do is the heat pain tolerance test. Again, each trial will be at

a different spot on your forearm. During this test, the probe will start out slightly warm. The temperature will then begin slowly increasing, and I'd like you to go as long as you can, and then indicate when the heat pain has reached the maximum you can tolerate by clicking the LEFT button on this mouse. Pressing the LEFT button will turn the heat off, so don't press it until the heat becomes intolerable. We'll repeat this procedure several times. Do you have any questions?"

Exercise Manipulation Protocol: Participants randomly assigned to the exercise training group will undergo aerobic exercise training 3 times/wk for 6 wks. To enhance and monitor adherence, all of the exercise sessions will be conducted at the Dayani Center and supervised by ACSM certified personal trainers thoroughly trained in study procedures. Each exercise session will consist of a 5 minute warm-up, 30 minutes of aerobic exercise, followed by a 5 minute cool-down period. Aerobic exercise will consist of treadmill walking/running, stepping, elliptical, or cycling exercise as preferred by the participant. This will allow participants to choose the type of aerobic exercise most tolerable to them to minimize symptom exacerbation (i.e., acute increases in pain) while maximizing adherence to the training program. Effort levels across the different types of aerobic exercise will be standardized using heart rate (HR) and perceived exertion (RPE) monitoring as recommended by the American College of Sports Medicine (ACSM). Target heart rate zones will be established using the Karvonen formula and heart rate reserve (HRR). Duration of exercise will be standardized at 30 minutes with a target exercise intensity between 70-85% HRR (RPE = 15, hard). Because of the focus on de-conditioned individuals with CLBP, the duration and intensity of exercise will be progressively increased up to target during the first two weeks to avoid symptom exacerbation and minimize study drop-out. Participants will begin with 10-15 minutes of exercise between 40-55% HRR (RPE = 11-12, light) during the first week, 20-30 minutes of exercise between 55-70% HRR (RPE = 12-13, somewhat hard) during the second week, and then 30 minutes of exercise between 70-85% HRR (RPE= 14-16, hard) for the duration of the study. To ensure that participants are exercising within their prescribed workload during each session, HR and RPE will be assessed and recorded every 5 minutes during exercise using Polar HR monitors and Borg's 6-20 RPE scale. In addition, pain will be assessed every 5 minutes during exercise using a pain rating scale developed for this purpose to monitor back pain, with adjustments to the workload in the event of back pain during exercise.

Endocannabinoid Assay Protocol: Outside of the participants' laboratory sessions, we will also separately conduct in vitro assessment of plasma endocannabinoid levels from sampled blood. All samples will remain de-identified using only assigned study subject numbers. Assays will be carried out on plasma extracted from blood samples designated for this purpose obtained before and after the 6 week exercise intervention (sessions 1 and 4 only). Assays will be conducted under the supervision of Co-Investigator [name] (Univ. of Wisconsin), given her prior experience with these assays⁷³. The endocannabinoids N-arachidonylethanolamine (AEA) and 2-arachidonoylglycerol (2-AG), key endogenous agonists of the CB1 receptor, as well as 4 structural lipid analogs (palmitoylethanolamide [PEA], oleoylethanolamide [OEA], N-docosahexaenoylethanolamine [DEA], and 2-oleoylglycerol [2-OG]), will be quantified using isotope-dilution, liquid chromatography–electrospray ionization–mass spectrometry based on published methods.

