A key finding in Bruehl et al.¹⁸ was that morphine reduced evoked pain responsiveness among individuals lower in EO function to levels statistically comparable to those observed in participants with higher spontaneous EO function *in the absence of any morphine*. We propose that these findings fit what we term an "opioid supplement model," in which opioid analgesics supplement EO function, making up the difference necessary to maximize opioid receptor-mediated pain inhibition. If the opioid supplement model is valid, then the desired degree of pain relief might be obtained by a combination of lower EO activity and higher amounts of opioid analgesics, or conversely – and in most cases preferably - higher EO activity and lower amounts of opioid analgesics. In this latter context, we propose that aerobic exercise may be used to enhance EO function, with subsequent beneficial effects on the dose of opioid analgesic needed to achieve desired pain relief.

Rationale for use of an aerobic exercise manipulation to enhance EO function derives from several sources. First, aerobic exercise is used clinically in CP management, and results of a number of controlled studies document that it significantly reduces evoked pain responses and clinical pain intensity in CP patients^{46,72,94,103,107}. Second, a review by Co-Inv [name] documents the analgesic effects of exercise with regard to laboratory evoked pain responses⁷⁶, with several opioid blockade studies conducted in individuals free of CP supporting a role for enhanced EO activity in these effects^{55,68,74,98,99}. These latter studies demonstrated that reductions in evoked pain responsiveness induced by acute exercise when healthy subjects are administered placebo do not occur when EO function is blocked by pharmacological opioid antagonists. Third, recent brain imaging research also supports these findings,

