indicating that an acute exercise manipulation reduced evoked pain responses and enhanced pain-related brain activations in an important EO pain modulatory brain region (periaqueductal gray), with parallel increases in circulating levels of beta-endorphin, a key EO analgesic¹⁰⁴. Fourth, potential importance of EO mechanisms in reducing CP via regular aerobic exercise training is suggested by opioid blockade work in animals. Regular exercise (from 5 days to 5 weeks) was found to significantly reduce, via EO mechanisms, behavioral indicators of CP in animal models of chronic muscle pain and neuropathic pain^{6,110}. Interestingly, significantly increased brain levels of beta-endorphin were noted during the exercise period, with exercise-related analgesia persisting for 5 days following exercise discontinuation¹¹⁰. The latter finding is particularly intriguing, as it suggests that regular aerobic exercise training may enhance EO function not only immediately after acute exercise, but for an extended period of time after acute exercise has ceased. Recently published work in humans further indicates that self-reports of greater physical activity, including exercise, is associated with enhanced conditioned pain modulation⁹⁶, a marker of descending pain inhibitory function which some work suggests has an EO-mediated component^{75,122}.

Plasma endocannabinoid levels will be assayed in vitro from blood samples obtained in the study. Endocannabinoids can produce analgesia, may potentially interact with and influence opioid responses (thus serving as a potential confound to tests of primary study hypotheses), and may represent a previously unexplored mechanisms of change for analgesic effects of exercise.⁷³ .

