5.0 Enrollment/Randomization

Participants will be recruited from a list of potentially qualifying participants from past studies in our lab who had previously indicated a desire to be contacted about future studies, as well as via local newspaper advertising, posted flyers (including at the Vanderbilt Interventional Pain Center and the Osher Center for Integrative Medicine at Vanderbilt), and e-mail advertisements distributed throughout campus via the Vanderbilt mass e-mail system. Interested individuals will be able to contact the designated study research assistant by phone or e-mail. Random assignment to both study conditions will be stratified by community vs. clinic population recruitment source to control for possible influence of this variable on results. Approximately equal numbers of males and females of all races will be recruited for the study. Individuals expressing an interest will first be provided verbally with information on the study procedures, risks, and benefits, and if interested, will be given the opportunity to read the IRB-approved informed consent form. All questions from potential subjects will be answered by the study representative as accurately as possible. All individuals agreeing to participate will provide written informed consent prior to beginning any study procedures. Subject recruitment and consent procedures will be carried out by individuals designated and trained by the PIs and the IRB to carry out these procedures (i.e., the research assistant).

The study will employ a mixed between/within-subjects design using double-blind, counterbalanced, placebo-controlled administration of both an opioid antagonist (naloxone) and an opioid agonist (morphine). The study will use a 6 week supervised aerobic exercise manipulation, with subjects randomly assigned to the exercise protocol or a no exercise control condition. All participants will undergo three identical laboratory pain-induction sessions (each \approx 5 days apart) prior to randomization to experimental condition, and again at the end of the 6 week exercise manipulation period (regardless of exercise group assignment) during which they will receive the 3 study drugs and participate in controlled laboratory evaluation of evoked thermal pain responsiveness.

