Blockade effect variables reflecting EO function will be derived by subtracting evoked pain responses during placebo from comparable responses during opioid blockade (separately for pre-manipulation baseline [BL] and post-manipulation). Given no theoretical rationale for expecting dose response effects with repeated dosing for placebo or naloxone conditions, we will average over the 4 pain stimuli within each of these drug conditions (separately for pre- and post-manipulation sessions) as a means of reducing random measurement error in deriving blockade effects. Blockade effects will be derived such that larger positive values reflect greater EO analgesia. To reduce number of variables, a mean value of the standardized EO function variables (blockade effects) will be derived and will be used initially in analyses (as in Bruehl et al.¹⁸). Chronic pain intensity pre- and post-manipulation will be defined as mean chronic pain ratings during the respective electronic diary sampling periods. As manipulation checks, we will determine whether degree of spontaneous EO function pre-manipulation is correlated significantly with evoked pain sensitivity and chronic pain intensity at BL. Total number of exercise minutes recorded during the post-intervention diary monitoring period (obtained in both groups) will be explored as a potential covariate for use in primary group analyses.

Primary Analyses.

Aim 1: To determine whether an aerobic exercise manipulation increases EO activity in CLBP patients, and whether these EO changes mediate manipulation-induced reductions in evoked pain responsiveness and daily CP intensity. We will conduct Group (exercise, control) x Time (BL, post-manipulation) mixed design ANOVAs to determine whether evoked pain sensitivity and CP intensity decreased significantly in the aerobic exercise group only. We will also conduct Group (exercise, control) x Time (BL, post-manipulation) mixed design ANOVAs on EO function (blockade effect variables pre- and

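### Recent exercise is neither standardised nor recorded at the lab visits, so a bout shortly before the post-manipulation placebo session could be read as a training effect on EO function

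*Combined protocol and SAP*

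**What the plan says.** **Instructions on exercise.** Under Exercise Manipulation in section 6.0, controls "will be asked to continue their current activity levels and not engage in any additional exercise activity during the study period", to be confirmed by diary. Exercise-arm participants complete 18 supervised sessions ("3 exercise sessions per week for 6 weeks"). No text says what they should do once these are finished.

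**Timing.** Training falls in Weeks 4 to 10, and section 6.0 puts Lab Visits 4-6 at about Weeks 11-12. Section 5.0 says only that the lab sessions are repeated "and again at the end of the 6 week exercise manipulation period (regardless of exercise group assignment"). No minimum or target interval from the last session to Visit 4 is given.

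**Visit procedures.** Visits 4-6 follow "Identical procedures to those described above for Lab Visits 1-3. Drug order is again randomized and counterbalanced". The steps listed for Visits 1-3 include a urine screen, five minutes of seated rest, cannulation and dosing. They contain no rule on exercise beforehand and no question about it.

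**Mechanism.** Section 3.0 reports that, in healthy subjects, pain reductions after acute exercise seen under placebo "do not occur when EO function is blocked by pharmacological opioid antagonists". It then distinguishes this from the effect of interest, namely that regular training "may enhance EO function not only immediately after acute exercise, but for an extended period of time after acute exercise has ceased". Section 10.0 describes EO function as mediating the acute effect in part.

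**Analysis.** Section 10.0 defines EO function as the naloxone-session response minus the placebo-session response, before and after the manipulation. The one related safeguard is "Total number of exercise minutes recorded during the post-intervention diary monitoring period", which will be explored as a possible covariate. That diary period is five days between Visits 4 and 5.

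**The concern.** The EO score is a difference between two sessions on different days. If a participant exercises shortly before the post-manipulation placebo session, the opioid part of the acute response lowers placebo pain and so raises the score. An equal bout before the naloxone session does not cancel this, because that opioid response is blocked.

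Such bouts are unlikely to be balanced between arms. One arm has just finished six weeks of training and has no instruction for the weeks that follow. The other has been asked not to add exercise for the whole study. The expected imbalance favours the hypothesis.

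At stake is the interpretation of the Group x Time result on EO function, which is the first test under Aim 1. The change in EO function is also the proposed mediator in all three aims. Without a record of time since last exercise, a positive result cannot be cleanly attributed to training rather than to a recent bout.

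**Working it through.** **1. The plan's own figure.** Section 10.0 gives d = 0.93 (r = 0.42) for the exercise effect on EO function, N = 116, and power above 0.90 at two-sided 0.05. Section 7.0 assigns half the participants to exercise, so there are 58 per arm.

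- r = d / √(d² + 4) = 0.93 / √(0.8649 + 4) = 0.42, which matches.
- Noncentrality = d × √(n/2) = 0.93 × √29 = 5.01 on 114 df, giving power 0.999. This is consistent with the stated figure.

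The sample size is not in question. This d comes from acute-exercise studies in healthy people, so it is the documents' own estimate of the acute effect that could enter the score.

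**2. Set-up.** Assume no training effect. Let f be the share of the exercise arm who exercise shortly before the post-manipulation placebo session, with no controls doing so. Let k be the share of the acute effect still present in the EO score, and ρ the pre-post correlation of that score. In change-score SD units the spurious group difference is

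δ = f × k × 0.93 / √(2(1 − ρ)).

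The documents give no value for f, k or ρ; all three are assumptions. With k = 1 and ρ = 0.5 the divisor is 1, so 0.93 applies directly in change-score SD units. The SD is held fixed.

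**3. Rejection probability** (two-sided 0.05, 58 per arm, noncentral t; 5% would be nominal).

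| Assumptions | f = 10% | f = 20% | f = 30% |
|---|---|---|---|
| k = 1, ρ = 0.5: δ | 0.093 | 0.186 | 0.279 |
| k = 1, ρ = 0.5 | 7.9% | 16.8% | 31.9% |
| k = 1, ρ = 0 | 6.4% | 10.8% | 18.4% |
| k = 0.5, ρ = 0.5 | 5.7% | 7.9% | 11.6% |
| k = 0.5, ρ = 0 | 5.4% | 6.4% | 8.2% |

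Example: f = 20%, k = 1, ρ = 0.5 gives δ = 0.2 × 0.93 = 0.186, noncentrality 0.186 × √29 = 1.00, and rejection 16.8%.

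**4. Range of the acute effect.** Section 10.0 reports source studies from d = 0.6 to 1.2. With k = 1 and ρ = 0.5, rejection is 6.2%-9.8% at f = 10%, 9.8%-24.9% at f = 20% and 16.1%-48.5% at f = 30%.

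**5. Diary coverage.** The five diary days lie between Visits 4 and 5. They may inform the run-up to Visit 5, but they miss the period before Visit 4 and probably that before Visit 6. Drug order is randomised, so the placebo session may be any of the three. The planned variable is total minutes, which does not give the time from the last bout to the session. It is also measured after randomisation and can be changed by the intervention.

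**The case against.** **The schedule already separates training from testing.** A reader might infer that the exercise arm is still training during Visits 4-6, or is expressly allowed to exercise on visit days. The documents support neither. Training is scheduled to end in Week 10, and freedom to exercise is an inference from silence. Participants were also selected for low activity. This narrows the route to a late last session or self-directed exercise, but does not close it: Week 10 runs straight into Week 11 and no interval is stated.

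**Controls have no visit-day ban.** They may continue their usual activity, so the asymmetry lies in the likelihood of exercise, not in a visit-day rule applied to one arm. This stands.

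**The bias need not run one way.** Section 10.0 treats the acute effect as only partly opioid, and section 3.0 names endocannabinoids as another possible mechanism. Any non-opioid part of a bout before the naloxone session lowers naloxone-session pain and hence the EO score. This stands.

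**The upper figures are generous.** They apply an effect from healthy people tested after acute exercise to back-pain patients who rest and are cannulated first, and whose responses are averaged over four pain tasks. They also need ρ = 0.5. This stands.

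**Mediation is partly protected.** It might be inferred that a spurious EO difference would produce false mediation in all three aims. Section 10.0 tests mediation only where exercise changes the outcome itself, and an indirect effect also needs a link from EO change to that outcome. The direct exposure is the EO group comparison.

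**The data might be recoverable.** The diary is prompted twice daily and may partly cover Visit 5, so it would be too strong to say that nothing could be done afterwards. Coverage of the other two visits would still be lacking.

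**Conclusion.** The gap is real and moderate in importance. The plan leaves the exercise arm's behaviour after session 18, the interval to Visit 4, and exercise before every lab visit unspecified and unrecorded. Its own account of acute exercise gives a route by which a recent bout could appear as improved EO function.

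The size cannot be determined from the documents. For f between 10% and 30%, the false-positive rate of the EO Group x Time test runs from about 8-32% (full acute effect, ρ = 0.5) down to about 5-8% (half the effect, ρ = 0). The first range is an upper-end illustration, not a central estimate. All of these figures assume no training effect, no such bouts among controls, and no offset from non-opioid analgesia on the naloxone day.

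The documents do not show that the bias will occur. They show that the trial as planned could neither prevent it nor rule it out, although doing so would cost very little.

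**What to change.** 1. State the interval between the last supervised session and Lab Visit 4, and say what exercise-arm participants are asked to do between session 18 and Visit 6.
2. Give both arms the same instruction for all six lab visits: no exercise on the visit day before the session.
3. At each visit, alongside the urine screen, record hours since last moderate or vigorous activity.
4. Keep the primary EO analysis on all randomised participants. Report the EO group difference by recent exercise, or with affected placebo and naloxone sessions excluded, as a supportive sensitivity analysis only. Say in the plan that it conditions on behaviour after randomisation, and that excluding either session removes that participant's EO score at that time point.

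The cost is a line or two of instructions, one question per visit, one extra analysis and an occasional rescheduled visit. The sample size does not change.
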